3.10 Blood pressure (BP) measurement by SAMSUNG *smartwatch* versus standard device

smartwatch will first be calibrated **SAMSUNG** for BP measurement following the instructions of the equipment itself. From then on, 8 consecutive measurements will be taken, at rest, alternating between using the *smartwatch* **SAMSUNG** and the arm pressure gauge (Brand *Welch*) standard, which uses aneroid meter and pulse auscultation (stethoscope *littman clinic*). Measurements with the standard device will be performed with the patient in the supine position, after 10 minutes of rest with 3 consecutive measurements. Additionally, a measurement will be performed in a sitting position and another measurement in an orthostatic position with a 30-second difference between measurements.

This assessment will be repeated in phase 5 of the project, following the same methodology described above.

3. 11 Definition of alerts – teleassisted group

The multidisciplinary team will receive alerts through the application platform, according to pre-established limits of blood pressure, heart rate and blood oxygen saturation.

- Blood pressure

Normal Parameters: Systolic [100 – 140 mmHg] and diastolic [70-90 mmHg]

Yellow Alert: Systolic [100 – 180 mmHg] and diastolic [90 – 110 mmHg]

Red Alert: Systolic [<90 and >180 mmHg] and diastolic [<60 mmHg and >100 mmHg].

- Heart Rate:

Normal parameters: HR detection between 60-100 bpm.

Red Alert: Detection of HR < 50 bpm outside sleep period; or HR > 100 bpm (concurrently assessed by watch)

- Oxygen Saturation:

Normal parameters: 95 – 100%

Yellow Alert: 91 – 95%

Red Alert: <90%

The conduct and actions planned to be taken by the clinical team after receiving the alerts through the Si3 platform (on D+1), as well as the guidelines that teleassisted patients will receive at the time of hospital discharge, are described in the table below:

INFORMAÇÕES AO PACIENTE

INFORMAÇÕES À EQUIPE CLÍNICA

[figure not shown]
	SITUAÇÃO	ORIENTAÇÃO	INTERVENÇÃO	AÇÃO
	Detecção de FC < 50 bpm fora do período de sono	Realizar medidas de parâmetros indiretos (ECG, P.A. E SPO ²)	Entrar em contato com a enfermeira da equipe pelo telefone	Analisar os parâmetros clínicos e os sintomas do paciente. Enfermeira aciona teleconsulta com o médico se necessário. Em caso de necessidade, o médico orienta o paciente a procurar o PS do InCor

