	Detecção de FC > 100	Realizar medidas de parâmetros indiretos (ECG, P.A. E SPO ²)	Entrar em contato com a enfermeira informando o ocorrido	Orienta o paciente a procurar o PS do InCor
	PAS: Sistólica < 90 e > 180 mmHg	Realizar medidas de parâmetros indiretos (ECG, P.A. E SPO ²)	-	Orienta o paciente a procurar o PS do InCor
	PAS: Diastólica < 60 e > 110 mmHg	Realizar medidas de parâmetros indiretos (ECG, P.A. E SPO ²)	-	Orienta o paciente a procurar o PS do InCor
	PAS: Sistólica 140 - 180 mmHg	Realizar medidas de parâmetros indiretos (ECG, P.A. E SPO ²)	Entrar em contato com a enfermeira da equipe pelo telefone	Analisar os parâmetros clínicos e os sintomas do paciente. Enfermeira aciona teleconsulta com o médico se necessário. Em caso de necessidade, o médico orienta o paciente a procurar o PS do InCor
	PAS: Diastólica 90 - 110 mmHg	Realizar medidas de parâmetros indiretos (ECG, P.A. E SPO ²)	Entrar em contato com a enfermeira da equipe pelo telefone	Analisar os parâmetros clínicos e os sintomas do paciente. Enfermeira aciona teleconsulta com o médico se necessário. Em caso de necessidade, o médico orienta o paciente a procurar o PS do InCor
	SPO ² : 91 - 95%	Realizar medidas de parâmetros indiretos (ECG, P.A. E SPO ²)	Entrar em contato com a enfermeira da equipe pelo telefone	Analisar os parâmetros clínicos e os sintomas do paciente. Enfermeira aciona teleconsulta com o médico se necessário. Em caso de necessidade, o médico orienta o paciente a procurar o PS do InCor
	SPO ² : <90%	Realizar medidas de parâmetros indiretos (ECG, P.A. E SPO ²)	Entrar em contato com a enfermeira da equipe pelo telefone	Orienta o paciente a procurar o PS do InCor
	Sono: < 7 horas contínuas	N/A	Entrar em contato com a enfermeira da equipe pelo telefone	Analisa a possível causa e fornece orientação de Higiene do Sono
	Passos: <500 passos	N/A	Entrar em contato com a enfermeira da equipe pelo telefone	Analisa a possível causa e orienta o paciente a aumentar o nº de passos

Table 2. Flow of care for patients in the study (alerts, guidelines, interventions and actions)

The institutional electronic medical record (Si3) software modeling that will be used in the project to access clinical and functional information regarding patient data, are exemplified in the figures below:

Figure 6. Institutional Electronic Health Record: Macro view of the alerts referring to the teleassisted group .

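### The Section 3.11 alert list and Table 2 give different cut-offs for yellow systolic and upper red diastolic pressure, and an SpO2 of exactly 90% falls between two alert bands with no prescribed action

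*Combined protocol and SAP*

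**What the plan says.** Section 3.11 lists the limits at which the multidisciplinary team is alerted about a tele-assisted patient. For blood pressure it gives three bands. The one that calls for no alert is "Normal Parameters: Systolic [100 – 140 mmHg] and diastolic [70-90 mmHg". The intermediate one, which shares its lower systolic edge with the band before it, is "Yellow Alert: Systolic [100 – 180 mmHg] and diastolic [90 – 110 mmHg". The most serious, with a low and a high limit for each component, is "Red Alert: Systolic [<90 and >180 mmHg] and diastolic [<60 mmHg and >100 mmHg".

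For oxygen saturation, normal is 95–100%, the intermediate band is 91–95%, and red is below 90%. For heart rate, normal is 60–100 bpm, and red is below 50 outside sleep or above 100.

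The same section says that the team's actions after an alert, and the guidance patients receive at discharge, "are described in the table below". That table is Table 2, in Portuguese, with separate rows for systolic and diastolic pressure. The systolic row "PAS: Sistólica 140 - 180 mmHg" leads to nurse contact, with a teleconsultation and then the emergency service only if needed; the diastolic row "PAS: Diastólica 90 - 110 mmHg" leads to the same response. By contrast, the row "PAS: Diastólica < 60 e > 110 mmHg" sends the patient to the emergency service, as does systolic below 90 or above 180. For SpO2, 91–95% gets nurse contact and below 90% gets emergency referral.

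**The concern.** The list governs what the team sees and Table 2 governs what is done, so they need to share the same limits. They differ on the lower edge of yellow systolic (100 against 140) and the upper edge of red diastolic (100 against 110). The list also contradicts itself in both places. Separately, one SpO2 value between two actionable ones has been left out of both.

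These are safety limits for people at home in the 30 ± 3 days after discharge from cardiac surgery. They are also part of the tele-assisted intervention, so the protocol should fix one version that others could reproduce. Section 3.5 says the platform is still to be developed as part of the project, so whoever configures it from this text would have to choose between two printed rules.

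**Working it through.** The plan gives no calculated figure to reproduce. The check sets the two sets of limits side by side.

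**Inputs.** The bands in the Section 3.11 list and the rows of Table 2, as quoted or described above.

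**Method.** Each band is treated as an interval that includes its printed end points; limits printed with < or > are strict. The *and* between a low and a high red limit is read as *or*, since no value can meet both. Systolic and diastolic are judged separately, as in Table 2. Whole numbers were stepped through for systolic 60–220, diastolic 30–140, SpO2 80–100 and heart rate 30–160.

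| Measure | Range | List | Table 2 |
|---|---|---|---|
| Systolic | <90 | red | emergency |
| | 90–99 | none | no row |
| | 100–139 | normal and yellow | no row |
| | 140 | normal and yellow | nurse |
| | 141–180 | yellow | nurse |
| | >180 | red | emergency |
| Diastolic | <60 | red | emergency |
| | 60–69 | none | no row |
| | 70–89 | normal | no row |
| | 90 | normal and yellow | nurse |
| | 91–100 | yellow | nurse |
| | 101–110 | yellow and red | nurse |
| | >110 | red | emergency |
| SpO2 | <90 | red | emergency |
| | 90 | none | no row |
| | 91–94 | yellow | nurse |
| | 95 | normal and yellow | nurse |
| | 96–100 | normal | no row |
| Heart rate | <50 (outside sleep) | red | nurse |
| | 50–59 | none | no row |
| | 60–100 | normal | no row |
| | >100 | red | emergency |

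**Results.**

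1. *Yellow systolic.* The list and Table 2 differ over 100–139 mmHg, which is 139 − 100 + 1 = 40 whole-number values. Within the list, normal and yellow overlap over 100–140. A systolic of 120 is both normal and yellow, and Table 2 asks for nothing.
2. *Upper red diastolic.* The list and Table 2 differ over 101–110 mmHg, which is 110 − 101 + 1 = 10 values. A diastolic of 105 is both yellow and red in the list; Table 2 gives nurse contact.
3. *SpO2 90%.* There is no band and no row, although 91% gets nurse contact and 89% gets emergency referral.
4. *Everything else.* Red systolic, yellow diastolic, lower red diastolic, both SpO2 alert limits and the heart rate limits are printed the same in both places.

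These counts are values on the scale, not patients or readings.

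**The case against.** **The list joins systolic and diastolic with *and*, so the overlaps may not exist.** Under strict pairing the 101–110 yellow/red overlap does disappear, and normal and yellow meet only at diastolic 90. But a reading of 190/85 then has no colour in the list while Table 2 refers it to the emergency service, and 150/80 has no colour while Table 2 asks for nurse contact. The list and Table 2 still disagree, and Table 2's separate rows point to separate judgement anyway. The SpO2 gap does not depend on this reading.

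**Red need not mean emergency referral.** This stands. Table 2 uses no colour words, and a heart rate below 50 outside sleep is red in the list but gets nurse contact in Table 2. A reader might infer that a red diastolic of 105 with nurse contact breaks a rule that red means emergency; the documents state no such rule. What remains is the list's own overlap and the different printed cut-off.

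**SpO2 90% is not the only unassigned value.** This also stands: systolic 90–99, diastolic 60–69 and heart rate 50–59 have no band and no row. They lie between an alert and the normal band, so silence there could be intended. The 90% value lies between two alert bands, where silence makes no sense.

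**The blood pressure differences look like typing or translation slips, and Table 2 gives one action for each value it covers.** Probably so, and this limits their weight. It does not settle which limits are to be displayed.

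**Conclusion.** Wrong as written. Two blood pressure limits conflict between the list and Table 2, and one SpO2 value between two actionable ones has no prescribed response. The blood pressure conflicts mainly affect which alert is shown, because Table 2 still fixes the action. The SpO2 gap affects the action itself and is the more important for safety, though it is a single value.

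The reading of the blood pressure bands assumes that systolic and diastolic are judged separately; the SpO2 finding assumes whole-number readings.

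A reader might go further and infer that patients will be mismanaged, that alerts will be inflated, or that re-hospitalisation will be distorted. The documents support none of these: they give no distribution of readings, and the actual Si3 settings are not visible in the text. The point is worth fixing before the platform is configured; it does not threaten the trial's validity.

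**What to change.** Make one edit to Section 3.11 and Table 2, with clinical confirmation of the values, before the platform is configured:

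- Set yellow systolic to 140–180, yellow diastolic to 90–110, and red diastolic to below 60 or above 110.
- End the normal bands at systolic 139 and diastolic 89.
- Start normal SpO2 above 95%, which agrees with the definition of normal oximetry in Section 3.9.
- State that systolic and diastolic are judged separately, and put *or* between the low and high red limits.
- Assign SpO2 90% in both the list and Table 2: red at 90% or below, or alternatively yellow at 90–95%. The choice is clinical.
- Confirm that systolic 90–99, diastolic 60–69 and heart rate 50–59 are meant to raise no alert, and that a heart rate below 50 is meant to be red with nurse contact.

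With these limits no whole-number blood pressure or SpO2 value falls in two bands, and the list and Table 2 share the same blood pressure and SpO2 alert limits. The cost is amendment wording and a check of the Si3 configuration against it; no extra patients or visits are needed.

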3.4 Selection of volunteers

Patients with heart disease undergoing cardiac surgery, monitored at the InCor outpatient clinic. Randomization will be performed 1:1 using an electronic randomization system and subsequently stratified from the RedCap platform, without knowledge by the team involved in the study. Patients will be randomized to intervention group (teleassisted group) or control group (standard follow-up of the institution)

1. **Control group (N=50):** patients with heart disease who underwent a surgical procedure with standard outpatient and post-surgical follow-up, according to institutional routines and protocols;
2. **Tele-assisted group (N=50):** patients with heart disease undergoing a surgical procedure remotely monitored through *smartwatch* and application.

Adult patients will be included, of both sexes, and ethnic profile representative of the Brazilian population, characteristic of the user population of the Unified Health System (SUS).

re-hospitalization rate, through scheduled consultations and extra interurrences (clock x institutional standard). As secondary outcomes will be evaluated: technological and treatment adherence, through the use of the mobile application by patients and development and implementation of the telemonitoring platform.

The goal is the inclusion of 40 patients/month (in all, in the 2 study groups: Remotely monitored watch group and group without a watch, following the institutional standard, following the randomization order generated by a specific

system) with 20 in each group of the study. In addition, the inclusion of patients will happen gradually and continuously, with 1 patient per group/working day.

Sem 1	Sem 2	Sem 3	Sem 4	Sem 5	Sem 6	Sem 7	Sem 8	Sem 9
1 ao 5	6 ao 10	11 ao 15	16 ao 20	21 ao 25	26 ao 30	31 ao 35	36 ao 40	41 ao 45
						1 ao 3	4 ao 8	9 ao 13
Sem 10	Sem 11	Sem 12	Sem 13	Sem 14	Sem 15	Sem 16	Sem 17	
46 ao 50								
14 ao 18	19 ao 23	24 ao 28	29 ao 33	34 ao 38	39 ao 43	44 ao 48	49 ao 50	
● Inclusão ● Retorno								

Figure 3. Flow of inclusion of patients in each arm of the study.

The remote patient monitoring flowchart to be used in this project is shown in Figure 3. Briefly, it includes:

1. Preoperative outpatient consultation with complete anamnesis to verify eligibility for using the **SAMSUNG™ Galaxy Watch5 Smartwatch**;
2. Hospitalization, surgery and collection of intraoperative data;

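### Section 3.11 gives inconsistent blood pressure alert limits: red diastolic is >100 mmHg in the list but >110 in Table 2, and the list's yellow bands overlap its red and normal bands

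*Combined protocol and SAP*

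**What the plan says.** Section 3.11 states the blood pressure limits twice for the teleassisted arm: once as a list of normal, yellow and red bands, and once in Table 2, which pairs each situation with guidance, intervention and action.

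- List, normal: "Normal Parameters: Systolic [100 – 140 mmHg] and diastolic [70-90 mmHg".
- List, yellow: "Yellow Alert: Systolic [100 – 180 mmHg] and diastolic [90 – 110 mmHg".
- List, red: "Red Alert: Systolic [<90 and >180 mmHg] and diastolic [<60 mmHg and >100 mmHg".
- Table 2, nurse analysis, with a teleconsultation and PS referral by the physician if needed: "PAS: Sistólica 140 - 180 mmHg" and "PAS: Diastólica 90 - 110 mmHg".
- Table 2, direct referral to the InCor PS: "PAS: Diastólica < 60 e > 110 mmHg". The matching systolic row uses <90 and >180 mmHg, as the list does.

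**The concern.** A monitoring protocol needs one limit for each level of response. Here the upper red diastolic limit takes two values. Within the list, one diastolic reading can be yellow and red at once, and one systolic reading can be normal and yellow at once.

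The people at risk are patients recently discharged after cardiac surgery. Staff working from the list would treat a diastolic of 105 mmHg as red, while staff working from Table 2 would start with nurse analysis. Whoever sets up the platform or writes the discharge guidance has to choose between the two without instruction from the protocol. A platform set from the list alone would also flag a systolic of 120 mmHg as yellow, and Table 2 has no row for that reading.

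**Working it through.** **Inputs.** All limits come from the section 3.11 list and Table 2. The check uses whole-mmHg values with inclusive bounds and takes each component separately. The conjunction inside the red limits is read as *or*, since one reading cannot be both below 90 and above 180. The Table 2 rows carry no colour label in the text reviewed. The >110 row is matched to red because it shares the lower limit of 60 with the list's red line and has the same action as the red systolic row.

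**Diastolic**

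| mmHg | List | Table 2 |
|---|---|---|
| <60 | red | direct PS referral |
| 60-69 | no band | no row |
| 70-89 | normal | no row |
| 90 | normal and yellow | nurse analysis |
| 91-100 | yellow | nurse analysis |
| 101-110 | yellow and red | nurse analysis |
| >110 | red | direct PS referral |

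Yellow/red overlap: 110 − 101 + 1 = 10 values. The same 10 values are where the list's red limit and Table 2's direct-referral limit disagree. The upper boundary is stated four times. It is 110 in three of them (list yellow, Table 2 nurse row, Table 2 direct-referral row) and 100 in one (list red).

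**Systolic**

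| mmHg | List | Table 2 |
|---|---|---|
| <90 | red | direct PS referral |
| 90-99 | no band | no row |
| 100-139 | normal and yellow | no row |
| 140 | normal and yellow | nurse analysis |
| 141-180 | yellow | nurse analysis |
| >180 | red | direct PS referral |

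Normal/yellow overlap: 140 − 100 + 1 = 41 values, which is the whole normal band. Of these, 139 − 100 + 1 = 40 have no row in Table 2. The red systolic limits agree in both places.

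**After aligning the list with Table 2** (red diastolic <60 or >110, yellow systolic 140-180): yellow and red no longer overlap, and the list and Table 2 agree. Normal and yellow still share two values, 140 systolic and 90 diastolic, so those endpoints need their own edit.

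**The case against.** The strongest reply is that these are two slips of the pen. The Table 2 blood pressure rows are coherent on their own, and in the list 100 may simply have been typed for 110 and for 140. That is plausible. It bears on how to correct the text, not on whether to correct it, because the list is part of the current protocol.

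Second, the list joins systolic and diastolic with *and*. Read as a joint condition, 120/80 would not be yellow, and the overlaps counted above would largely disappear. But then 190/80 would not be red in the list, whereas Table 2 refers on systolic pressure alone. Reading each component separately is the better fit. The differences in the stated figures (100 against 110, 100 against 140) remain on either reading.

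Third, a diastolic of 101-110 does not go unanswered. Table 2 gives it nurse analysis, and section 3.4 has patients told to seek the PS in cases the clinical team considers serious. Blood pressure is also collected manually (Table 1, phase 4), so an alert arises only when a reading is taken. This stands: the difference is between direct and clinician-mediated referral.

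Fourth, colour does not always fix the response. A heart rate below 50 bpm is red in the list but gets nurse analysis in Table 2. The point here needs no general colour rule. It rests on the matched <60 limit and on the overlap inside the list.

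Fifth, the values with no band (systolic 90-99, diastolic 60-69) may be intended to raise no alert. Heart rate 50-59 bpm is left open in the same way, so these gaps are a question and not an error.

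**Conclusion.** The inconsistency stands, as a contradiction in a safety threshold in the operative text. Its size is 10 diastolic values with two alert levels in the list and, with components read separately, 41 systolic values that are both normal and yellow. The documents give no alert rates and do not show the platform's actual settings, so the number of patients affected cannot be estimated.

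Three stronger readings are tempting but not supported:

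- *The limits distort the comparison between arms.* Section 3.4 names "re-hospitalization rate, through scheduled consultations and extra interurrences (clock x institutional standard" as an outcome, and alert-driven referral exists only in the teleassisted arm. But that referral is part of the intervention being compared, a PS visit is not in itself a re-hospitalization, and no rates are given. An effect on the comparison is speculation.
- *Patients with a diastolic of 101-110 are left without care.* Table 2 gives them a response.
- *Red alerts are seen a day late.* The phrase "after receiving the alerts through the Si3 platform (on D+1" is not defined in the text reviewed, and no actual delay can be derived from it.

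**What to change.** 1. Use one red diastolic limit. The default is to change >100 to >110 in the list, since the other three statements already use 110. If the clinical team prefers the more cautious >100, use it throughout: list yellow 90-100, Table 2 nurse row 90-100, Table 2 direct-referral row >100.
2. Change the list's yellow systolic band to 140-180, as in Table 2.
3. Assign systolic 140 and diastolic 90 to one band each. Yellow fits Table 2, whose nurse rows start at those values; normal would then be 100-139 and 70-89.
4. Set the platform and the discharge guidance to the same figures.
5. Optionally, confirm whether systolic 90-99 and diastolic 60-69 are meant to raise no alert.

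The cost is a few edits to the list (and two Table 2 rows if >100 is chosen), plus a check of the platform and the guidance. The sample size and analysis do not change. The choice of limit is clinical: >110 sends a diastolic of 101-110 through a nurse and not straight to the PS, while >100 means more PS referrals.

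### Alert limits in section 3.11 overlap and disagree with Table 2 for diastolic and systolic pressure, and an SpO2 of 90% triggers nothing in either place

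*Combined protocol and SAP*

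**What the plan says.** Section 3.11 states that the team is alerted "according to pre-established limits of blood pressure, heart rate and blood oxygen saturation". It sets three levels for blood pressure:

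- Readings that call for no alert are listed as "Normal Parameters: Systolic [100 – 140 mmHg] and diastolic [70-90 mmHg".
- The lower of the two alert levels is given as "Yellow Alert: Systolic [100 – 180 mmHg] and diastolic [90 – 110 mmHg".
- The higher alert level is given as "Red Alert: Systolic [<90 and >180 mmHg] and diastolic [<60 mmHg and >100 mmHg".

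For SpO2 the same list has "Normal parameters: 95 – 100" (per cent), then yellow at 91–95% and red below 90%.

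Table 2 is introduced as the team's conduct after an alert, together with the guidance given to patients at discharge. The row "PAS: Diastólica < 60 e > 110 mmHg" sends the patient to the InCor emergency service. The rows "PAS: Diastólica 90 - 110 mmHg" and "PAS: Sistólica 140 - 180 mmHg" go to the nurse, who calls in the doctor by teleconsultation if needed; the doctor can then refer to the emergency service. The SpO2 rows are 91–95% (nurse) and below 90% (emergency service). Heart rate below 50 outside sleep, which is red in 3.11, is on nurse review in Table 2. Heart rate above 100, also red, goes to the emergency service.

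Neither place says which list governs where the limits differ.

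**The concern.** The alerts are the working part of the intervention. Section 3.4 relies on the monitored parameters to find risk early in patients who are at home for 30 ± 3 days after cardiac surgery. Section 3.5 says that the platform is still to be built by the institution's IT team, so somebody has to turn these limits into code. With two lists that differ and no order of precedence, that person has to guess.

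What is at stake is patient handling. A diastolic of 105 may be shown as yellow or as red. An ordinary systolic of 120 may raise a yellow alert for which no response is written. An SpO2 of 90% may pass in silence between two values that each call for action.

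**Working it through.** No sample-size or error-rate figure is involved. The check assigns each whole value to every band that contains it and sets the result beside the Table 2 row. End points are taken as inclusive. The *and* in the red limits is read as *or*: a systolic cannot be both below 90 and above 180, and Table 2 gives systolic and diastolic separate rows.

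| Reading | Section 3.11 | Table 2 |
|---|---|---|
| Diastolic 90 | normal and yellow | nurse |
| Diastolic 91–100 | yellow | nurse |
| Diastolic 101–110 | yellow and red | nurse |
| Diastolic above 110 | red | emergency |
| Systolic 100–139 | normal and yellow | no row |
| Systolic 140 | normal and yellow | nurse |
| Systolic 141–180 | yellow | nurse |
| SpO2 95% | normal and yellow | nurse |
| SpO2 91–94% | yellow | nurse |
| SpO2 90% | no band | no row |
| SpO2 below 90% | red | emergency |
| HR below 50, outside sleep | red | nurse |
| HR above 100 | red | emergency |

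1. **Diastolic.** Yellow (90–110) and red (above 100) intersect at 101–110, which is 110 − 101 + 1 = 10 whole values. Table 2 draws its line at 110.
2. **Systolic.** Normal (100–140) lies wholly inside yellow (100–180): 140 − 100 + 1 = 41 values, the entire normal band. Table 2 starts at 140, so 100–139 (40 values) meets the yellow limit without any written response.
3. **SpO2.** Yellow stops at 91% and red starts below 90%. Table 2 repeats both limits, so it cannot close the gap at 90%. A reading of 90% gets less response than the better reading of 91%.
4. **Shared end points.** Systolic 140, diastolic 90 and SpO2 95% are each normal and yellow. Table 2 puts all three on nurse review.
5. **After the change proposed below.** Systolic runs 100–139, 140–180, then below 90 or above 180. Diastolic runs 70–89, 90–110, then below 60 or above 110. SpO2 runs 96–100%, 91–95%, then 90% or below. No value has two colours, and SpO2 has no gap.

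The counts show how wide each overlap is. They say nothing about how often patients produce such readings, because the protocol gives no reading frequency.

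**The case against.** **Table 2 settles the action.** Section 3.11 assigns colours, and it points to the table for conduct. Table 2 gives exactly one response to a diastolic of 105. This stands. A reader might infer that 105 leads to two stated actions, emergency referral because it is red and nurse review by the table. The text does not support that: nowhere does it equate red with emergency referral, and heart rate below 50 is red with nurse review. The diastolic conflict is therefore one of colour and trigger.

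**These are slips.** Systolic 100 for 140 and diastolic 100 for 110 look like typing or translation errors. That is plausible, but nothing says that Table 2 overrides the section that defines the alerts. It also cannot explain SpO2 90%, where both places agree.

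**Other values also lack a colour.** Systolic 90–99, diastolic 60–69 and HR 50–59 have no band in 3.11 and no row in Table 2. A reader might count these as further errors. The two places agree that no alert is raised, and this may be deliberate.

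**There is a safety net, and the configuration may be right.** Section 3.4 has the team following the parameters themselves, with teleconsultation and referral available. That softens the consequence. The figures accompanying Table 2 could not be read here; row colours might appear there. How Si3 is actually configured is not documented, so a claim that the platform is wrong would go too far.

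**Conclusion.** The point holds for the written rule at three places: diastolic 101–110 has two colours, systolic yellow swallows the normal band, and SpO2 90% has neither an alert nor a response. The last is the most serious, since it is an action gap that neither list repairs. The other two leave the coder without a single rule for when an alert fires and at what level.

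A reader might go further and infer a distortion of re-hospitalisation or unscheduled visits in the teleassisted arm. The documents do not support that: they show neither the platform configuration nor the number of readings. No effect on trial outcomes is claimed, and no statistical figure changes. This is a correction that should be made, chiefly for patient safety.

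The conclusion assumes whole-unit readings, inclusive end points and *or* in the red limits. If the watch reports fractions of a per cent, the SpO2 gap runs from 90% up to 91%.

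**What to change.** Replace the limits in section 3.11 with:

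- Systolic: normal 100–139, yellow 140–180, red below 90 *or* above 180 mmHg.
- Diastolic: normal 70–89, yellow 90–110, red below 60 *or* above 110 mmHg.
- SpO2: normal 96–100%, yellow 91–95%, red 90% or below.

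State that systolic and diastolic each trigger alone. In Table 2, change the lower SpO2 row from below 90% to 90% or below. If the platform handles fractional SpO2, write yellow as above 90% up to 95%, and normal as above 95%.

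The clinical team should sign off these limits. If it prefers red diastolic above 100, yellow becomes 90–100 and both Table 2 diastolic rows change to match. In the same step it should confirm that no alert is intended for systolic 90–99, diastolic 60–69 and HR 50–59.

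Before the first patient is monitored, test Si3 with systolic 95, 120 and 140; diastolic 65, 90, 105 and 111; HR 55; and SpO2 90% and 95%.

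The cost is one revised list, one changed limit in Table 2, a clinical sign-off and a short configuration test.

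### Heart rate above 100 bpm is red from the first beat above normal and leads only to emergency referral, and diastolic pressure of 101 to 110 mmHg is both yellow and red

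*Combined protocol and SAP*

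**What the plan says.** **Heart rate.** Section 3.11 gives "Normal parameters: HR detection between 60-100 bpm" and then "Red Alert: Detection of HR < 50 bpm outside sleep period; or HR > 100 bpm (concurrently assessed by watch". Heart rate has no yellow band; blood pressure and oxygen saturation each have one.

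**Actions in Table 2 (in Portuguese).** For HR below 50 the team's action is "Analisar os parâmetros clínicos e os sintomas do paciente. Enfermeira aciona teleconsulta com o médico se necessário": analyse the clinical parameters and symptoms, with the nurse starting a teleconsultation if needed. The cell ends with the physician sending the patient to the PS only if necessary. For HR above 100 the row asks for an ECG, blood pressure and SpO2, then "Entrar em contato com a enfermeira informando o ocorrido" (tell the nurse what happened). The team's action is only "Orienta o paciente a procurar o PS do InCor" (advise the patient to go to the PS). The same action stands alone for "PAS: Sistólica < 90 e > 180 mmHg", for "PAS: Diastólica < 60 e > 110 mmHg" and for SpO2 below 90%.

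**Diastolic pressure.** The red limit in 3.11 is "diastolic [<60 mmHg and >100 mmHg", while the red row in Table 2 begins above 110. The yellow band is 90 to 110 mmHg in both places.

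**Related text.** Section 3.4 item 7 plans teleconsultation when a problem is detected and keeps the PS for cases the team judges serious. Table 1 (Phase 4) lists heart rate as collected automatically, and blood pressure and ECG as manual. Section 3.8 on device provision has the watch worn day and night. Section 3.11 says the team receives the alerts on D+1.

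**The concern.** Alert limits and the actions attached to them are the intervention in the tele-assisted arm, so they should lead each reading to one action. Two of them do not do this cleanly.

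(a) HR above 100 has the least buffer of any red limit, on a signal that is recorded without the patient doing anything. Its listed action has no review step. HR below 50 has the same colour but does get review, so the table treats the two ends of one measurement differently without giving a reason. Staff working from item 7 and staff working from Table 2 could handle the same tachycardia alert in different ways.

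(b) A diastolic reading between the two red limits has two colours within 3.11 itself. The yellow action is nurse review; the red action is PS referral.

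At stake is consistent, proportionate handling of patients in the weeks after cardiac surgery, and a clear description of what the intervention was.

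**Working it through.** The plan states no alert or referral rate, so there is no figure to reproduce. The check sets the limits and actions side by side.

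**Step 1. Distance from the end of normal to the start of red.** Gap = |red limit − nearest end of the normal range|, with the limits from 3.11 and Table 2.

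| Limit | Normal ends | Red starts | Gap |
|---|---|---|---|
| HR high | 100 | above 100 | 0 bpm |
| HR low | 60 | below 50 | 10 bpm |
| Systolic high | 140 | above 180 | 40 mmHg |
| Systolic low | 100 | below 90 | 10 mmHg |
| Diastolic high, 3.11 | 90 | above 100 | 10 mmHg |
| Diastolic high, Table 2 | 90 | above 110 | 20 mmHg |
| Diastolic low | 70 | below 60 | 10 mmHg |
| SpO2 | 95 | below 90 | 5 points |

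HR high is the only limit with a gap of zero.

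**Step 2. Conditions on the trigger.** The low HR limit applies only when the patient is awake. The high limit states no condition on rest or duration. The closing parenthesis of the heart-rate alert might be meant as a confirming reading, but it is not explained and does not appear in Table 2.

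**Step 3. Actions for the two red heart-rate rows.**

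| | HR below 50 | HR above 100 |
|---|---|---|
| Readings requested | ECG, BP, SpO2 | ECG, BP, SpO2 |
| Contact with nurse | yes | yes |
| Review of parameters and symptoms | yes | not listed |
| Teleconsultation if needed | yes | not listed |
| PS | if needed | always |

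The left column follows the sequence in 3.4 item 7; the right column does not. Read literally, a patient at 45 bpm while awake is reviewed first. A patient at 101 bpm, in sinus rhythm on the watch ECG and without symptoms, is sent to the PS.

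**Step 4. Diastolic overlap.** Take 105 mmHg.
- 3.11 yellow (90 to 110): met.
- 3.11 red (above 100): also met.
- Table 2 review row (90 to 110): met.
- Table 2 red row (above 110): not met.

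The overlap is 110 − 100 = 10 mmHg, that is, readings of 101 to 110. Three of the four stated limits (yellow in 3.11, and both rows in Table 2) put the boundary at 110. Only the red line of 3.11 puts it at 100.

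**Step 5. Size.** The documents give the number of monitored patients (50) and the period (30 ± 3 days), but not how often HR exceeds 100. The number of referrals therefore cannot be calculated.

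**The case against.** The strongest defence is that Table 2 is the team's judgement of seriousness made in advance. Section 3.11 presents the limits as set beforehand and the table as the team's planned conduct. On that reading item 7 and the table agree, and a PS instruction is itself guidance to the patient. This largely stands. Four of the five red rows end only in PS referral, and a reader might infer that all four contradict item 7. The documents do not support that: the systolic, diastolic and SpO2 limits can reasonably count as serious in themselves. What remains is that no text says so, and that the HR below 50 row shows red does not always mean serious.

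Three other points stand in part.
- Referral is not immediate in every sense. The HR above 100 and SpO2 rows include contact with the nurse, and the parenthesis may imply confirmation. The 101 bpm example is therefore a literal reading, not a prediction of practice.
- A reader might infer that the requested ECG is ignored. The action cell is only silent about it; 3.4 item 6 has the team monitoring the collected parameters, and the other direct-referral rows are equally silent.
- Some figures, and the row colours of Table 2, cannot be seen in the available text. Red status here is taken from 3.11.

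There is also a safety argument for referring without waiting for the watch ECG: its accuracy is a study objective. A rule that kept immediate referral for AF alone would miss the flutter, re-entry and wide-QRS tachycardias that the case report form lists. This does not justify leaving the row unchanged, but it limits how far the fix may go.

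**Conclusion.** The point holds for two stated rules: the HR above 100 row, and the red diastolic limit in 3.11. The first has a zero gap from normal and lacks the review step that the plan gives its other red heart-rate alert. The second conflicts with Table 2 and with 3.11's own yellow band over 10 mmHg.

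Two stronger conclusions are tempting and are not supported. One is that HR above 100 will produce the most needless PS visits. The zero gap, automatic recording and lack of a rest condition make this plausible, but no alert rate is given, so it is an inference. The other is that the rule distorts the re-hospitalization comparison. Visits prompted by alerts are part of the strategy under test, and the outcome sentence in 3.4 is incomplete in the available text, so no effect can be claimed or sized.

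The weight is minor to moderate. The conclusion assumes that staff would apply Table 2 as written and that no unseen figure supplies the missing step.

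**What to change.** 1. **HR above 100 row of Table 2.** Use the action text of the HR below 50 row. Keep the 100 bpm limit. Keep immediate PS referral for any of:
   - symptoms;
   - any non-sinus or unclassified tachycardia on the watch ECG, not AF alone;
   - an unreadable ECG when the nurse or physician cannot be reached promptly;
   - another red value.

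   State what the parenthesis in 3.11 means and carry it into Table 2, or delete it.
2. **Start of the review.** Because alerts reach the team on D+1, say that the patient's same-day call to the nurse starts the review.
3. **Red diastolic limit in 3.11.** Change it to above 110 mmHg, to match Table 2 and the yellow band.
4. **Section 3.4 item 7.** Add one sentence saying that the red systolic, diastolic and SpO2 limits are pre-set as serious and lead to PS referral.

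The cost is one action cell with its exceptions, one corrected limit and a few sentences. No extra patients, visits or devices are needed. The downside is nurse and teleconsultation time, and some delay for HR above 100 patients who meet none of the immediate-referral conditions. The delay stays acceptable only if the same-day call works, so step 2 is a necessary part of the change.
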